#### 5. SAMPLE SIZE CONSIDERATIONS

Sample size calculations were produced using the proc power function in SAS Version 9.4. These were conducted to achieve 80% power to detect a difference in the active arm versus the control group at the 5% level of significance. Based on a mean of 99mg/L in the control group and a common standard deviation of 62mg/L derived from the literature [2, 3], a total sample size of 90 participants would provide sufficient power to detect a greater than a 40% relative difference for CRP in the dornase alfa group compared to the control group. Given the reported average values in severe and non-severe participants and on clinical observations from COVID-19 patients, this difference would be achievable and clinically relevant.

This study will use existing data collected at UCLH from participants admitted with COVID-19 as a comparator group. Participants in the database will be selected to act as controls as follows:

- Apply the inclusion and exclusion criteria of the COVASE study where the appropriate data are available
- Additional selection to identify closest matches

This will give the correct ratio of active versus comparator (ratio of 1:2). To achieve the required power, this would result in 30 participants in the active treatment group and at least 60 in the control. An additional 10 participants will be recruited as a control for the exploratory objectives

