#### **11.1 Primary endpoint analysis**

#### **Exploristics Limited**

### Identifier: EXP20012 Clinical Study Identifier: 132333

The primary endpoint will be compared between groups using a repeated measures mixed model, adjusted for age, gender, BMI, baseline CRP value (defined as the last CRP measurement prior to randomisation, or the first CRP following Dexamethasone for HCs), time from baseline, and whether they have a key comorbidity, defined as one or more of hypertension, diabetes or cardiovascular disease. An interaction between treatment and time from baseline will also be included in the model. CRP measurements more than 7 days after randomisation (or date of first CRP measurement following Dexamethasone initiation for HCs) will be removed from the analysis, so the comparison is over 7 days.

Due to the treatment by time interaction effect being included in the model, examining the treatment effect alone would be an inappropriate comparison, therefore the least squares means and 95% confidence intervals at the mean follow-up time will be compared between arms, which will take into account both the treatment effect and the treatment by time interaction. These means will be presented on the real scale, e.g. taking the antilog of the least squares mean if the dependent variable has been log-transformed. The difference between the least squares means (on the scale the model was fitted) and the standard error of the difference will be used to generate a treatment z-score, which will be compared against the normal distribution with mean 0 and variance 1, to obtain the two-sided p-value.

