In addition, a supplementary analysis will be conducted where the area under the log(CRP) curve will be calculated for each individual up to 7 days of follow-up, divided by the number of days that the individual has been followed up for, to get a standardised area under the curve. The area will be calculated by assuming a linear line between the log(CRP) measurements, regardless of the time between measurements. If measurements are available after day 7, they will be excluded, and the last available log(CRP) measurement prior to day 7 will be used to calculate the area; for example, if the last measurement within 7 days of randomisation for a given individual was on day 4, but they have a day 10 measurement available, the area up to day 4 will be calculated, and divided by 4 to get the standardised area. A linear model will then be fitted, with standardised area under the log(CRP) curve as the outcome, adjusted for age, gender, BMI, log(baseline CRP value) (defined as the last log(CRP) measurement prior to randomisation, or the first log(CRP) following Dexamethasone for HCs) and whether they have a key comorbidity, defined as one or more of hypertension, diabetes or cardiovascular disease. A two-sided p-value will be calculated by comparing the z-score from the Wald test of the treatment effect against the normal distribution with mean 0 and variance 1.

Finally, as a supplementary analysis, the primary analysis will be performed, but including the HCs from the second propensity score matching analysis, where the matching was performed using the last pre-Dexamethasone CRP as opposed to the baseline CRP as defined above. The same model will be fitted for this analysis as the primary analysis, but the model will be adjusted for their last pre-Dexamethasone CRP as opposed to baseline CRP.

Prior to analysis, the primary endpoint will be assessed for conformance to normality assumptions and the appropriate transformation will be conducted if necessary. This model-based approach is likely to be more robust to missing or spurious data. Treatment effect will be declared significant at the 5% level of significance.

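### The primary CRP model has no fixed scale, and read literally it adjusts a possibly logged response for unlogged baseline CRP; log(CRP) with log(baseline CRP) can be specified now

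*SAP*

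**What the plan says.** On the response scale, SAP 11.1 states that "the primary endpoint will be assessed for conformance to normality assumptions and the appropriate transformation will be conducted if necessary". Protocol 11.3.2 carries the same rule. The antilog appears in SAP 11.1 only as an example of how means would be back-transformed if logs had been taken. The p-value comes from the difference in least squares means on whatever scale was fitted. One test decides the result: "Treatment effect will be declared significant at the 5% level of significance".

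On the baseline covariate, the primary model is "adjusted for age, gender, BMI, baseline CRP value", with time and key comorbidity. The supplementary AUC model in the same section has log(CRP) as its outcome and is "adjusted for age, gender, BMI, log(baseline CRP value" (logged) with the same comorbidity term. SAP 8.2 and the propensity model in SAP 11 list plain baseline CRP. SAP 9.2 applies the transformation rule to continuous endpoints and does not mention covariates.

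On planning, SAP 5 works in mg/L: "Based on a mean of 99mg/L in the control group and a common standard deviation of 62mg/L derived from the literature", with a 40% relative difference as the target. SAP 3 describes the trial as open-label, and SAP 12 runs the primary endpoint analysis at an interim after 12 randomised participants.

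**The concern.** The scale decides what is estimated (a difference in mean mg/L or a ratio of geometric means) and which p-value is compared with 5%. Here it is settled after outcome data exist, with treatment known, by a rule that two statisticians could apply differently. The interim also needs a scale, and nothing says that the interim choice binds the final analysis.

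The baseline covariate matters more than usual because most of the comparator group is historical. Adjustment for baseline CRP is part of the defence against confounding. If the response is logged and baseline is not, the covariate that probably predicts most strongly is fitted with the wrong shape. Some of its information is lost, and a difference in baseline between the groups is not fully removed.

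**Working it through.** **Inputs.** From SAP 5: control mean 99, common SD 62, 40% relative difference (so 0.4 × 99 = 39.6 and an active mean of 59.4), 30 active and 60 control, two-sided 5%. From Protocol 7.1.1: CRP at least 30 mg/L at entry. Assumptions not in the documents: lognormal CRP, equal coefficient of variation (CV) in both arms, and a log-log baseline correlation of 0.5–0.7 except where another value is stated.

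**1. The plan's own figure.** Noncentrality = 39.6 / (62 × √(1/30 + 1/60)) = 39.6 / 13.86 = 2.86 on 88 degrees of freedom. Exact t power is 80.7% at 90 and 79.3% at 87. The stated 90 reproduces.

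**2. Can raw CRP be normal under these figures?**
- Control: Φ(−99/62) = Φ(−1.60) = 5.5% below zero.
- Active: Φ(−59.4/62) = Φ(−0.96) = 16.9% below zero.

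CRP cannot be negative. A lognormal with mean 99 and SD 62 has log SD √ln(1 + (62/99)²) = √ln 1.392 = 0.575 and skewness 2.1. A 40% fall becomes ln 0.6 = −0.511.

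**3. Cost of a raw baseline in a log model.** Let c be the correlation between log(baseline) and baseline. For a lognormal, c² = 0.575² / (62/99)² = 0.331/0.392 = 0.844. Residual variance relative to using log(baseline) is (1 − ρ²c²)/(1 − ρ²):
- ρ = 0.5: 0.789/0.75 = 1.05
- ρ = 0.7: 0.587/0.51 = 1.15

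The entry floor of 30 mg/L trims the lower tail. Simulation with that floor gives inflation of about 3–10% at ρ = 0.5–0.7, and 17% at 0.8. In standard-error terms 3–10% is √1.03 to √1.10, or 1.5–5%. If group baselines differ by 20–30%, raw adjustment leaves about 1–2% bias in the ratio; log adjustment leaves essentially none.

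**4. Type I error.** Simulated trials had 30 active and 70 controls, one post-baseline value and a z reference.
- Rule followed as written (log if normality is rejected): log is chosen in about 93–99% of trials, and error stays near 5%.
- Scale chosen by significance: about 6.5–7.2% with the floor, and 7.1–7.5% without it at correlations 0.3–0.7. This is roughly two points above either scale used alone.

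**5. Power for a 40% fall, same simulation at correlation 0.6.**

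| Response / baseline | Power |
|---|---|
| raw / raw | 98.8% |
| log / raw | 99.6% |
| log / log | 99.8% |

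At correlation 0.3, without the floor, the figures are 96.4%, 98.6% and 98.8%.

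**The case against.** The case against has real substance.

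- **The rule depends on distribution, not on p-values.** It is to be applied before analysis, and SAP 9.2 adds homogeneity of variance. On data as skewed as these it leaves almost no freedom. This stands: the 6.5–7% is a worst case in which the rule is ignored. A reader might infer that the wording invites choosing the significant scale, but nothing in the documents suggests that intent.
- **The SAP is silent on baseline scale rather than explicit.** Sections 8.2 and 11.1 define which measurement is baseline. Where the SAP does fix a log response, it logs baseline too, which may show the intention. This stands as a reading of intent. It does not remove the gap, because the two models in one section are worded differently and SAP 9.2 covers endpoints only.
- **The negative tails concern individual values, whereas the model needs roughly normal residuals.** Correct. The tail areas are strong indirect evidence, not proof. The text also does not say whether values or residuals are to be checked, so it cannot be faulted for testing the wrong one.
- **A logistic propensity model needs no normal covariate.** Correct; a log there is optional.

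A reader might also infer that a raw-scale model would lose much of the power. The documents do not support that: step 5 shows about one point at correlation 0.6 and about 2.4 at 0.3. Comparing the planned 80.7% with the 97.5% that an unadjusted log analysis gives at 30 against 60 is not like for like. The second figure assumes equal CV, which shrinks the active SD to 0.6 × 62 = 37.2 mg/L.

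**Conclusion.** The concern holds as a matter of specification. The scale of the single confirmatory test is left to an unspecified check on open-label data, and the baseline covariate is worded inconsistently with the SAP's own AUC model. The documents already contain the reasons to choose logs: planning figures that a normal model cannot fit, an effect stated as a ratio, and a log-scale supplementary analysis.

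The numerical stakes are modest: 3–10% of residual variance, 1–2% bias for a 20–30% baseline gap, and a worst-case two points of type I error that would not arise if the rule were followed. These sizes rest on lognormal CRP with CV 62/99, a log-linear baseline relation and one post-baseline value; the trial has repeated values. The floor at 30 mg/L is also approximate, since it applies at eligibility, while the analysis baseline for historical controls is the first CRP after dexamethasone.

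Neither the sample size nor the power is undermined. The change is worth making because it is free and fixes what the trial estimates.

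**What to change.** In SAP 8.1, 8.2 and 11.1, state that the response is log(CRP), that the covariate is log(baseline CRP), and that the treatment effect is reported as a ratio of geometric means with its 95% confidence interval. State that the same scale is used at the interim. Keep residual checks as diagnostics that do not change the primary model, and give the untransformed analysis as a named sensitivity analysis. Align Protocol 11.3.2, or record the difference as a clarification. Say how any CRP reported below the assay limit is entered before logging. Using log(baseline CRP) in the propensity model is optional.

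The cost is a few sentences of SAP text. No extra data, participants or visits are needed.

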#### **Exploristics Limited**

#### **11.2 Secondary endpoint analyses**

This study was not powered to detect any effects relating to secondary endpoints. Therefore, the secondary analysis will involve descriptive statistics. In general, continuous data will be summarised using the number of individuals, mean (standard deviation), median (1st and 3rd quartiles), minimum and maximum, and categorical data will be represented as frequency counts (percentages).

A further comparison of the secondary endpoints will involve the appropriate general linear models.

For the following secondary endpoints, the same model will be fitted as for the primary endpoint, except with the dependent variable as the secondary endpoint, and adjusting for the baseline level of the secondary endpoint, as opposed to baseline CRP (baseline defined as the last measurement prior to randomisation, or the first measurement following Dexamethasone for HCs):

- Levels of acute phase reactant CRP over 35 days follow-up. The difference from the primary analysis model is that observations will be included up to 35 days after baseline. The treatment comparison will be at the mean follow-up time.
- White blood cell count over 7 days follow-up
- Neutrophil count over 7 days follow-up
- Lymphocyte count over 7 days follow-up
- Monocyte count over 7 days follow-up
- Eosinophil count over 7 days follow-up
- Basophil count over 7 days follow-up
- Procalcitonin over 7 days follow-up
- D-dimer count over 7 days follow-up
- Ordinal score (WHO scoring tool) over 7 days follow-up (using randomized individuals only)

For the following secondary endpoints, a survival analysis will be conducted. The number of events by arm will be compared. The time to event data will be censored at 28 days post last dose (Day35) for the randomised participants and at 35 days after baseline, or the date of the last electronic record, whichever is earlier, for the historical control group. If median time-to-event times exist, the Kaplan-Meier method will be used to estimate the median time-to-event times and the associated 95% confidence intervals. The survival model will include treatment as a stratification variable and significance assessed using a log-rank test. A Cox proportional hazards model will be used to generate a hazard ratio and associated confidence intervals, adjusting for age, baseline CRP value (defined as the last CRP measurement prior to randomisation, or the first CRP following Dexamethasone for HCs) and treatment as a main effect. For the time to discharge from hospital analysis, data will be censored if the participant dies prior to discharge at the date of death.

- Survival at Day35
- Time to discharge from hospital from baseline (days) to Day 35

For the following secondary endpoint, a logistic regression model will be fitted, with age, gender, BMI baseline CRP value (defined as the last CRP measurement prior to randomisation, or the first CRP

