8.3.1 Dose modifications

Based on clinical judgement, it may be decided to extend the dosing period for some participants. For example, a change from 2.5mg BID for 7 days to 2.5mg BID for up to 14 days. In particular, if participants have significant benefits from therapy, but show relapses of the COVID-19 inflammatory state (rising CRP and increasing oxygen requirements in the absence of bacterial infection), on completing 7 days of treatment, then the medical team have the choice of reinstating dornase alfa treatment for up to 7 further days (14 days in total) at 2.5mg BID. Blood sampling will continue until the last day of dosing with dornase alfa.

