#### Figure 1: COVASE Trial Schematic

Participants will be screened, consented, enrolled and randomised up to 3 days after they are admitted to the hospital. They will be randomised in a 3:1 ratio to receive BAC + dornase alfa or BAC alone. A total of 40 participants will be enrolled (30 to receive BAC plus dornase alfa and 10 to receive BAC). On Day1 to Day7 of the trial, participants randomised to the active arm, will receive 2.5mg BID nebulised dornase alfa in addition to BAC. On Day1, Day3, Day5 and Day7, blood samples will be drawn in both trial arms in order to test pharmacodynamic endpoints (PD), biomarkers and clin labs. Clinical assessments will be undertaken daily (as per UCLH clinical guidelines). Participants will be followed until discharge or death or a maximum of 28 days follow-up.

A sample size re-estimation is planned when 12 randomised participants have completed Day7 of follow-up. This analysis will ensure that the assumptions made in the sample size calculation remain valid. However, if the variability is higher than expected then up to an additional 10 participants will be enrolled and treated with dornase alfa (up to 48 participants in total).

CRP has been chosen as the Primary Endpoint because it is a clinically important marker of inflammation and is used to make clinical treatment decisions. In addition, it is induced by the overexuberant inflammation mediated by the NETs and inflammatory histones. CRP is a prognostic marker and correlates with clinical symptoms, inflammation and response to therapy.

Based on clinical judgement, it may be decided to keep some participants on treatment for up to 14 days. In particular, if participants have significant benefits from therapy, but show relapses of the COVID-19 inflammatory state (rising CRP and increasing oxygen requirements in the absence of bacterial infection), on completing 7 days of treatment, then the medical team have the choice of

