#### **Exploristics Limited**

### Identifier: EXP20012 Clinical Study Identifier: 132333

reinstating dornase alfa treatment for up to 7 further days (14 days in total). Blood sampling, as specified, will continue until the last day of dosing with dornase alfa.

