#### Study controls

Due to the evolving situation with hospitalised COVID-19 participants, the burden on the NHS and the availability of other COVID-19 trials, it is considered inappropriate to conduct a placebocontrolled study. Therefore, a randomised, controlled, open-label approach where dornase alfa is administered on top of BAC and compared to BAC alone has been adopted.

The data derived from the 10 participants who are randomised to the BAC arm of the study who do not receive dornase alfa will provide control data for all of the study endpoints.

Figure 2 Comparator Data. **10** participants Primary endpoints randomised to BAC Secondary endpoints alone Exploratory endpoints 30 participants  $\geq$  60 BAC matched Primary endpoints randomised to BAC historic COVID-19 Secondary endpoints + dornase alpha controls Approximately 10 participants on BAC Exploratory endpoints with bio-banked samples

The 30 participants randomized to BAC + dornase alfa will be compared to 10 randomised controls from the COVASE study. In addition, 10 participants in other clinical trials on BAC (bio-banked samples) and 60 participants from a historic database of the first 120 people with COVID-19 treated at UCLH will also be used as comparator data.

However, to enhance the control group, a hybrid approach will be applied such that additional data will be combined with the randomised controls, illustrated in Figure 2. The sample size calculation indicates that 90 evaluable participants are required (60 control:30 active). These control data may include: data from the randomised BAC arm, historic COVID-19 UCLH database, biobanked samples from other ongoing trials and observational trials in COVID-19. This hybrid strategy allows two things:

- provides comparators for all of the study objectives (including limited data for the exploratory objectives)
- demonstrates that the historic controls are representative/similar to the study population

Comparator data from UCLH is available as historic controls for the Primary and Secondary Endpoints. CRP is routinely measured daily (or on alternate days) in all participants admitted to UCLH and will be used to control for the Primary Endpoint. All of the Secondary Endpoints are also

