### 4. PLANNED ANALYSES

There are two planned analyses, an interim analysis after 12 randomised individuals have completed Day7 follow-up and the final analysis, once all randomised individuals have completed follow-up (which is the minimum of discharge, death or 35 days after randomisation). At the interim analysis, only the primary endpoint and safety data will be examined, and no secondary or exploratory endpoints. A promising zones approach [1] (see Section 12 for details) will be followed at the interim analysis stage to identify the conditional power and make a decision as to whether to continue enrolment up to the planned 40 individuals randomised, or whether to increase the planned sample size up to a maximum of 48 randomised individuals. See Section 12 for details.

After the final randomised participant has completed follow-up, a more complete analysis will be undertaken, including examination of endpoints relating to the primary, secondary and exploratory objectives. A full safety analysis will also be carried out at this stage.

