### 6.2 Per protocol population

The per protocol (PP) population will be all evaluable patients randomised to BAC + dornase alfa or BAC only, as well as matched historical comparators, excluding important protocol violations. Important protocol violations will be defined as:

- Initiated dornase-alfa prior to Dexmathasone.
- Withdrew from the study prior to 7 days follow-up.
- Discontinued the study drug prior to discharge from hospital or 7 days follow-up.

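### The censoring date for randomised participants is tied to the last dose, which gives the stated Day 35 only for a course ending on Day 7 and does not exist for the BAC arm

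*SAP*

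**What the plan says.** The rule stands in SAP 11.2 and, in the same words, in protocol 11.3.3: "The time to event data will be censored at 28 days post last dose (Day35) for the randomised participants". In the SAP it governs survival at Day 35 and time to discharge up to Day 35. Both are analysed with event counts by arm, Kaplan-Meier estimates, a log-rank test and an adjusted Cox model. For historical controls the SAP sets a cap of 35 days after baseline, or the end of the electronic record if sooner. The protocol gives controls only the end of the record.

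On course length the documents say:
- Planned course (SAP section 3): "On Day1 to Day7 of the trial, participants randomised to the active arm, will receive 2.5mg BID nebulised dornase alfa".
- Extension (protocol 8.3.1, repeated in SAP section 3): "then the medical team have the choice of reinstating dornase alfa treatment for up to 7 further days (14 days in total".
- Early stopping: protocol 8.8 lists reasons that include progression and toxicity, and SAP 6.2 counts as a protocol violation a patient who "Discontinued the study drug prior to discharge from hospital or 7 days follow-up".
- No course at all (SAP section 3, study controls): "10 participants who are randomised to the BAC arm of the study who do not receive dornase alfa".

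On the follow-up horizon:
- SAP section 4 defines completed follow-up as that "which is the minimum of discharge, death or 35 days after randomisation".
- SAP section 3 and protocol 5.1 say: "Participants will be followed until discharge or death or a maximum of 28 days follow-up".
- The blood-volume table in protocol 8.5 shows 35 days in the trial for BAC, for 7-day dosing and for 14-day dosing.
- Protocol Appendix 1 places the final visit at discharge or, at the latest, Day 35.
- SAP 2.2.2 takes mortality from the EPIC database for randomised participants and historical controls alike.

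**The concern.** A censoring date counted from the last dose is set by what happened after randomisation. Patients who stop because they are deteriorating would have a shorter window, and patients extended after a relapse a longer one. Kaplan-Meier, log-rank and Cox methods assume that censoring is unrelated to prognosis, and here it might not be. It would also sit badly with SAP section 6, which bases the primary analysis population on the ITT principle, because SAP 11.2 uses that population for the secondary endpoints.

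At stake is whether the mortality and discharge comparisons use the same window in all groups. Nothing in the text says which half of the rule governs when last dose plus 28 days and Day 35 differ. A programmer who coded last-dose date plus 28 would be following the plan as written.

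**Working it through.** **Step 1. Reproduce the plan's figure.** Censoring day = day of last dose + 28. For the planned course, 7 + 28 = 35. The stated Day 35 is reproduced exactly.

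**Step 2. Apply the same formula to the other courses the documents allow.**

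| Last dose | Last dose + 28 | Difference from Day 35 |
|---|---|---|
| Day 1 | Day 29 | -6 |
| Day 2 | Day 30 | -5 |
| Day 4 | Day 32 | -3 |
| Day 6 | Day 34 | -1 |
| Day 7 | Day 35 | 0 |
| Day 9 | Day 37 | +2 |
| Day 11 | Day 39 | +4 |
| Day 14 | Day 42 | +7 |
| None (BAC) | undefined | - |

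The literal range is 42 - 29 = 13 days. Day 42 is 7 days past the latest final visit in Appendix 1, and the date moves later still if there is a gap before dosing is reinstated.

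**Step 3. Who has a short course.** The per-protocol wording accepts dosing that ends at discharge, so early last doses can belong to patients who recovered quickly as well as to those who stopped for progression. The direction of any distortion therefore cannot be stated in advance.

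**Step 4. Set the groups side by side, on the literal reading of the SAP.**
- Dornase alfa arm (30 planned): Day 29 to Day 42, depending on doses received.
- Randomised BAC arm (10 planned): no date.
- Historical controls (60 planned): 35 days after baseline, or end of record if sooner.

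**Step 5. What one affected patient could do (illustration only).** Suppose a patient stops on Day 2 and dies on Day 33. The literal rule censors that patient alive at Day 30. If the other 29 patients in the arm are alive and followed to Day 35, estimated Day-35 survival is 100% instead of 29/30 = 96.7%, a difference of 1/30 = 3.3 percentage points. In the other direction, a Day-40 death in an extended patient leaves Day-35 survival unchanged but would be counted among the events by arm. If no comparator is still under observation by then, it adds nothing to the log-rank observed-minus-expected total.

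**Step 6. Day numbering.** If baseline is Day 1, 35 days after baseline is 1 + 35 = Day 36. The historical-control cap and study Day 35 then differ by one day even when the last dose is on Day 7.

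**The case against.** The strongest reply is that Day 35 is written into the sentence itself and is plainly what was meant: planned last dose on Day 7, plus 28, gives a nominal study day. Much supports this. The protocol 8.5 table gives 35 days in the trial for all three regimens, BAC and 14-day dosing included. Both endpoint names carry Day 35, so a later discharge falls outside the endpoint as named. The final visit is no later than Day 35, with no exception for extended dosing. EPIC supplies deaths whatever the dosing history. The 28-day maximum in protocol 5.1 and SAP section 3 follows a description of Day 1 to Day 7 dosing and may simply be the same 7 + 28. Finally, SAP 11.2 says the trial was not powered for secondary endpoints, and the 7-day CRP analysis is untouched.

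Most of this stands. A reader might infer that early stoppers and extended patients will in fact be censored on different dates, that BAC patients have no follow-up horizon, or that the survival comparison is biased. The documents support none of these: they show a common horizon elsewhere and give no rate of early stopping, extension or late death. What the reply does not remove is the rule itself. It names an event that varies between patients and that one randomised arm never has, and no sentence gives the bracketed day precedence.

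**Conclusion.** The point holds as a contradictory anchor in one sentence that appears in both documents. Its two halves agree only for a last dose on Day 7. If coded literally, it makes censoring depend on treatment received, over about Day 29 to Day 42, and leaves the randomised BAC arm without a date, while the SAP's historical controls have a fixed cap. If the bracketed Day 35 is taken as operative, every randomised participant has one common date and only the one-day numbering question remains.

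The effect is probably small. Only secondary endpoints are involved, and only events in roughly Days 29 to 42 among patients with a non-standard course could move. The 3.3-point figure assumes one such death among 30 patients with the rest alive and fully followed. It shows scale and is not a forecast. The correction is still worth making, because a log-rank test and a hazard ratio for mortality are planned and their window should not be open to choice.

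**What to change.** In SAP 11.2 and protocol 11.3.3, delete the reference to last dose. Censor every randomised participant, whatever the arm or doses received, at one fixed date counted from randomisation or baseline, with the same day numbering as the historical controls. State whether that date is Day 35 or 35 days after baseline.

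For survival, use EPIC vital status up to that date even after discharge or early stopping, and do not count events after it. SAP section 4 should not be cited as already providing this, because its definition of follow-up ends at discharge.

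Reconcile the 28-day maximum in protocol 5.1 and SAP section 3 with the chosen horizon by giving it a starting point or replacing it.

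The cost is wording in the two documents. No visits, samples or patients are added, the mortality source is already planned, and no change to dosing is implied.
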